A Pilot Study of *The CKM JumpStart Tool*

Funding Agency: Doris Duke Charitable Foundation

Award: Clinical Scientist Development Award

Principal Investigator: [name], MD

Protocol

2/15/2023

Abstract

Objective(s) and Hypotheses:

Conservative kidney management (CKM) is an important therapeutic alternative for patients who do not wish to pursue dialysis for their advanced chronic kidney disease (CKD). Conservatively managed patients can survive several years after their decision to pursue CKM and experience sustained quality of life until late in the course of illness.¹ Conservatively managed patients also spend less time in the hospital,²⁻⁵ less often experience burdensome procedures,^{2,5} and less often die in the hospital setting than patients treated with dialysis.⁵⁻⁹ Despite a growing body of evidence and clinical services to support patients who do not wish to pursue dialysis,^{10,11} patients rarely recall discussing more conservative options with their providers and are typically presented dialysis as the default treatment option for their advanced CKD.^{12,13} This study aims to test the acceptability and feasibility of a novel communicational tool, The CKM JumpStart Tool. We hypothesize that the CKM JumpStart Tool will be feasible and acceptable to patients with advanced CKD and their providers and will help to support informed and shared decision-making for treatment of advanced CKD.

Research Design:

This is a randomized pilot study of patients with advanced CKD and their close persons who are receiving care at University of Washington (UW) Medicine and VA Puget Sound Health Care System (VAPSHCS). The study utilizes medical record review, qualitative interviews, and standardized questionnaires to assess the feasibility and acceptability of the CKM JumpStart Tool and to explore differences in decisional conflict and goal concordant care between patients and who receive the decision aid and those who do not.

Methodology

We will recruit 76 patients aged 18 years and older with advanced CKD as defined as an estimated glomerular filtration rate (eGFR <25 ml/min/1.73m² from UW Medicine and VAPSHCS). We will randomize patients in a 1:1 fashion to either usual care or receipt of the CKM JumpStart Tool. Patients will complete study procedures by phone or in-person, over a total of 3 study visits. We will also recruit providers of patients who received the CKM JumpStart Tool about their experiences using the the CKM JumpStart Tool.

Relevance

An important step to towards helping patients choose the right treatment for them and their advanced CKD is to promote discussion of the different treatment options with their providers. The proposed study has the potential to lead to the creation of a cost-effective, time-saving and scalable intervention to improve the care of patients with advanced CKD.

List of Abbreviations

CKD: chronic kidney disease

Conservative Kidney Management: CKM

eGFR: estimated glomerular filtration rate

UW: University of Washington, Seattle WA

VAPSHCS: VA Puget Sound Health Care System, Seattle WA

KRI: Kidney Research Institute, University of Washington, Seattle WA

VACOIN: VA Center of Innovation, Seattle WA.

Contents

Protocol Title: A Pilot Study of *A Guide to Conservative Care* **Error! Bookmark not defined.**

1.0 Study Personnel..... 5

2.0 Introduction 5

3.0 Objectives 6

4.0 Resources and Personnel..... 6

2.0 Introduction

Chronic kidney disease (CKD) afflicts 1 in 7 Americans. Although dialysis is commonly regarded as a life-prolonging therapy for advanced CKD, there is growing recognition that dialysis is not always beneficial. Decisions about dialysis often involve difficult trade-offs between the potential gains in longevity and symptom management and the burdens of treatment including the

substantial time spent on dialysis, complications related to treatment, frequent interaction with healthcare system and loss of independence.

Conservative kidney management (CKM) is an important option for patients who choose not to pursue dialysis that focuses on slowing the decline in renal function, active symptom management, advance care planning and the provision of appropriate palliative care. Conservatively managed patients can survive several years after their decision to pursue CKM and experience sustained quality of life until late in the course of illness.¹ For adults aged ≥ 75 years with significant comorbidity and functional impairment, dialysis might not improve survival^{2,9,14-17} and quality of life¹⁸⁻²⁰ beyond what can be achieved with a more conservative approach for advanced CKD. Conservatively managed patients also spend less time in the hospital,²⁻⁵ less often experience burdensome procedures,^{2,5} and less often die in the hospital setting than patients treated with dialysis.⁵⁻⁹

Despite a growing body of evidence and clinical services to support patients who do not wish to pursue dialysis,^{10,11} patients rarely recall discussing more conservative options with their providers.^{12,13} Although it is a professional obligation that all available treatment options are discussed with patients,²¹ many providers find it difficult or are reluctant to discuss conservative options for advanced CKD.^{22,23} Qualitative interviews with providers suggest that many feel ill-equipped to have a conversation about CKM or worry that if they do not offer dialysis, it would be perceived as “no care” or “giving up.”^{10,22}

The current application is to support a pilot study to test the acceptability and feasibility of a novel communication tool to help providers “jumpstart” a conversation about CKM with their patients that was created by the principal investigator (PI, [name]). The CKM JumpStart Tool has the potential to be a cost-effective, time-saving and scalable intervention to improve the care of patients with advanced CKD.

3.0 Objectives

We aim to conduct a randomized pilot study to test the feasibility and acceptability of a novel communication tool, called The CKM JumpStart Tool, and explore preliminary outcomes, including decisional uncertainty and goal concordant care to inform a future clinical trial. We hypothesize that the decision aid will be feasible and acceptable to patients and their providers.

4.0 Resources and Personnel

Study Sites:

This study will involve VAPSHCS and the UW. Study subjects will be recruited from UW Medicine and VAPSHCS in Seattle. UW will be used only as a recruitment site for non-Veteran patients, and this protocol covers VA research activity only. Original study data collected with UW Medicine will be stored and at the KRI. Original study data collected at VAPSHCS will be stored at the VACOIN. Deidentified UW patient data will be moved to VA Puget Sound to facilitate pooled analysis. All data analyses will occur at VACOIN. No VA data will be shared with the UW.

Study Team Personnel

[name], Principal Investigator. She will provide overall project leadership and supervision of study performance and progress. She will oversee all aspects of the study subject

recruitment and follow-up, data collection and management, analyzing and interpreting data, and preparing study findings for publication and presentation. She will have access to protected health information.

[name], Research Coordinator: She will assist with contacting and recruiting subjects, obtaining subject informed consent, administering the intervention and surveys, interviewing subjects, and collecting and analyzing study data. She will have access to protected health information.

[name], BA, Research Coordinator: She will assist with all aspects of study coordination. She will also assist with recruitment and data collection and analysis. She will transcribe audio-recorded interviews collected for this study. She not have access to protected health information.

[name], Biostatistician: He will perform the data analysis. He will have access to protected health information.

5.0 Study Design

We will conduct a randomized pilot study to test the feasibility and acceptability of the CKM JumpStart Tool among patients with advanced kidney disease and their providers using interview methodology and questionnaires. We will also explore preliminary outcomes including decisional uncertainty and goal concordant care to inform a future clinical trial.

5.1 Study arms

Patients will be randomized in a 1:1 fashion using a random number generator (www.randomizer.org) to either 1 of 2 groups, CKM Jumpstart Tool or Usual Care. All enrolled patients will complete surveys within 2 weeks of their following clinic visit with their provider (T2), and about 3 months after this clinic visit (T3). All study procedures will be conducted either by phone or in-person, at the patient's convenience. Each visit will take about 20 minutes.

The CKM JumpStart Tool

The CKM JumpStart Tool is a 1-page handout that describes the values of a patient and words that a provider can try with the patient to explore the patient's values more and to provide a values-based introduction to CKM. The values describes in the CKM JumpStart Tool is based on a patient's response to a single validated question that asks the patient, if they had to choose, do they value care directed at longevity or comfort. A patient may also indicate whether they are unsure what kind of care they value more. Because there are 3 potential responses to the values question (longevity, comfort, unsure), there are 3 different versions of the CKM JumpStart Tool. (Appendix A.1 Intervention Materials: CKM JumpStart Tool Versions). The CKM JumpStart Tool does not contain any identifying information about the patient.

Patients who are randomized to receive the CKM Jumpstart Tool will be surveyed at T1. Using the patient's answer to the values question, study staff will generate a CKM JumpStart Tool prior to their upcoming clinic visit with their provider. Study staff will inform the patient that their response to the values question will be shared with their provider prior to their next clinic visit and that their providers might bring up their values and treatment options for kidney disease, if the

situation permits. We will share the CKM Jumpstool with their provider by encrypted email (Appendix A.2. Intervention Materials: Provider Email Notification) prior to the visit. The email will contain a link to a brief video demonstrating the use the CKM JumpStart Tool (bit.ly/CKMJumpstart) and an attachment which describes the study in more detail (Appendix B.8: Provider Study Information Document). We will also provide the providers with a paper copy of the CKM JumpStart Tool on the day of their visit with the patient and remind them how to use the CKM JumpStart Tool using a standard script (Appendix A.3. Intervention Materials: Provider Script Notification). In both in email and in-person, we will assure the provider that they are not obligated to use CKM JumpStart Tool or discuss their patient's values and CKM and that they are free to do so if they choose. We will also assure the provider that the patient consented to a potential discussion of their values and CKM if it should arise during their clinic visit.

Usual care

Patients randomized to usual care will also will be surveyed at T1 but **will not** have a CKM JumpStart Tool generated describing their values and their response to the values question will not be shared with their providers. They will receive care as they usually do from their provider.

5.2 Potential Risks and Benefits

Anticipated risks:

The principal risk posed to patients is the potential *loss of confidentiality*. The proposed work requires the collection of protected health information to identify and recruit eligible patients and contact and maintain follow up with participating patients. We will also audio-record interviews with subjects during which personal information might be spoken. To minimize this risk, we have outlined steps below to safeguard patient confidentiality. These include restricting data analyses to only de-identified data files, keeping separate a crosswalk file linking study ID with personal identifiers and data analysis files, storage of data on password-protected secure servers and key-locked filing cabinets accessible to only study team members who have completed training in the protection of human subjects, and the aggregation of study data for presentations and publications in order to conceal the subjects' identities.

It is possible that patients might feel *unease with discussing their illness experience*. To minimize discomfort, patients will be assured that they can decline to answer any question they wish and will be free to discontinue the interview at any time. All patients will be reminded that they have the right to refuse to withdraw from the study at any time.

It is possible that providers might worry that participation, not participating, and/or being candid in interviews might *affect their standing at work*. We will assure providers that their participation is entirely voluntary and that they are under no obligation to use the Tool or answer any question during the study. Their participation or lack thereof will not be reported to their supervisor, and we will keep all data collected on providers confidential. Any personal identifiers will be kept separate from the data collected and that analyses will only be conducted with de-identified data. Results will be reported in aggregate and therefore be anonymous.

Potential Benefits:

Patients and providers may benefit from this research directly and indirectly. This study will explicitly allow participants the opportunity to describe their experiences, which may give participants an important outlet for describing both their concerns and successes. Participants may also gain satisfaction from participating in a research project designed to improve the quality

of care for patients with advanced CKD, which gives a sense that they are active contributors to important quality improvement processes. For patients who know little or nothing about CKM, discussion about CKM can be an educational experience for them. For clinicians who find it difficult to engage in goals-of-care conversations and discuss CKM, they might also learn new communication skills modelled by the CKM JumpStart Tool.

With the measures outlined, we believe that the potential risks associated with the proposed work will be mitigated and will not outweigh the potential benefit to study subjects and the greater CKD population. The findings of this study will inform ongoing development of a novel communication tool to support shared decision-making for patients with advanced CKD and their providers.

5.3 Recruitment Methods

We aim to enroll up to 76 patients with advanced CKD and up to 30 of their providers in this study.

Patients

We are requesting a waiver of consent and HIPAA authorization to access the electronic medical records of patients to identify eligible patients for this study and to obtain their name and contact information for recruitment purposes only.

We will mail an *Introductory Letter* (see Appendix B.1: Recruitment Materials: Patient Introductory Letter) introducing the study. We will then follow up with a phone call about 1 week later to confirm that patients receive the letter, introduce the study, and determine if they are interested in participating in the study using a standard script (see Appendix B.2. Recruitment Materials: Patient Introductory Script).

We will not make more than 3 attempts to reach each patient by phone after mailing the introductory letter.

Providers

For enrolled patients who are randomized to the intervention, we will approach their providers in-person after their visit with their enrolled patients to inquire whether they had used the CKM Jumpstart Tool during their visit with the patient, and if so, invite them to participate in a brief phone or in-person interview about their experience using the CKM JumpStart Tool. We will use a standard script to recruit providers (Appendix B.3 Recruitment Materials: Provider Recruitment Script). If providers are unavailable to speak after the clinic visit, we will approach providers using encrypted email within 1 week after the clinic visit (Appendix B.4. Recruitment Materials: Provider Recruitment Email) and invite them complete an interview. We are requesting a waiver of informed consent to inquire providers if they had used the CKM Jumpstart Tool during their visit and the primary reason for not using the Tool to determine providers' eligibility to participate in the study.

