Decisional conflict (Appendix C.7): At T1, T2 and T3, patients will be asked to complete the 4-item SURE Test to assess their preference for dialysis vs. CKM and the decisional conflict they have about their options.^{28,29}

Post-clinic patient interview (Appendix C.8): At T2, patients assigned to the intervention will be invited to answer 4 open-ended questions about their clinical encounter with their provider. Questions will pertain to topics discussed during the encounter with their clinician, whether their provider asked them about their values, whether CKM was discussed, and their perception of CKM based on the conversation. Interviews will be audio-recorded then transcribed. We estimate that an interview will take 10-15 minutes to complete.

Documentation of discussion of CKM with patients: At T2 and T3, we will review each patient's recent nephrology clinic notes to determine whether providers documented a discussion with patients about CKM. Documentation will be transcribed into a Word document without personal identifiers.

Providers

Demographic information: From publicly available directories, we will ascertain providers' gender, race, and years since completing their medical degree.

Use of the CKM Jumpstart Tool (part of Appendix B.3): For providers whose patients were assigned to the intervention, we will ask them after their visit with their enrolled patient (T2) whether they had used the CKM Jumpstart Tool during their visit, and if not their reasons for not using the Tool.

Post-clinic provider interview (Appendix C.9): For providers who used the CKM Jumpstart Tool, we will ask 4 open-ended questions about their clinical encounter with the patient and their experience using the CKM JumpStart Tool. Clinician responses will be recorded in writing, then transcribed into a Word document. We estimate that an interview will take 5 minutes to complete. Interviews will be conducted by phone or in-person in a private clinic room or office of the provider, per the provider's preference. Providers will be offered a \$10 gift card for their participation.

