5.6 Data Analysis

Feasibility and acceptability: As our primary outcome, and measure of feasibility, we will compare the proportion of patients in each study arm who reported having discussed CKM with their provider at T2 and T3. Based on prior work, the rate of patient-reported discussion of CKM with their health care providers in usual care settings is approximately 3%. The target sample size (n=76) is estimated to provide 80% power (two tailed, $\alpha=0.05$) to detect an absolute difference of 25% or more in rates of patient-provider discussion of CKM between the intervention and control groups assuming a 30% attrition rate. We will also evaluate the proportion of patients in each arm who has documentation in their nephrology clinic notes that CKM was discussed with the patient at T2 and T3.

As a measure of acceptability, we collect attrition rates at T2 and T3. We will further assess user experience of the CKM JumpStart by performing a qualitative analysis of post-intervention interviews with patients and providers, coding for themes elucidating pros, cons and other considerations with using the CKM JumpStart Tool and discussion about CKM.

Exploratory outcomes: We will assess change (i.e., T3-T1 and T2-T1) in decision conflict about treatment decisions for advanced CKD and quality of communication scores. We will also assess change in the proportion of patients who reported receiving goal concordant care at each study time point based on patients.

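### The by-arm comparison of charted CKM discussion is open to bias toward the Tool: staff question only intervention-arm providers after the visit, and nothing requires the note to be finished first

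*Protocol*

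**What the plan says.** **Who is contacted.** Protocol section 5.3 (Recruitment Methods, Providers), for patients randomised to the intervention only: "we will approach their providers in-person after their visit with their enrolled patients to inquire whether they had used the CKM Jumpstart Tool". Providers who did not use it are asked for "the primary reason for not using the Tool to determine providers' eligibility to participate in the study".

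**Timing.** The only timing rule is the fallback: "If providers are unavailable to speak after the clinic visit, we will approach providers using encrypted email within 1 week after the clinic visit".

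**What follows for users.** Section 5.5 (Providers): "we will ask 4 open-ended questions about their clinical encounter with the patient and their experience using the CKM JumpStart Tool".

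**Usual care.** Section 5.1 generates no Tool for these patients and says "They will receive care as they usually do from their provider". No post-visit contact with their providers is described anywhere.

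**The outcome concerned.** Section 5.5 has staff review recent nephrology notes at T2 and T3 for a documented CKM discussion. Section 5.6 evaluates the "proportion of patients in each arm who has documentation in their nephrology clinic notes that CKM was discussed". It does so in addition to the primary outcome, which is patient-reported discussion.

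**The concern.** The post-visit question establishes Tool use and whether a provider can be interviewed. It is a recruitment and measurement step, not a component of the Tool. Yet it is put to one arm only, and it may reach the provider while the note for that visit is still unwritten. A provider who has just been asked about the Tool, why it was not used, or how the conversation went has a reason to mention CKM in the note that a usual-care provider does not have. A discussion that took place in either arm would then be more likely to be recorded in one of them.

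This matters because chart review is the only between-arm measure of CKM discussion that does not rely on patient report, so it is the natural cross-check on the primary outcome. Section 3.0 says that the pilot is to inform a later trial. A documentation rate raised partly by staff questioning would be a poor planning figure for a setting without that questioning.

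**Working it through.** **1. The sequence in each arm, from the protocol**

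| Step | Intervention | Usual care | Part of the Tool? |
|---|---|---|---|
| Email with video link and study document, before the visit (5.1) | Yes | No | Yes |
| Paper copy and scripted reminder on the visit day (5.1) | Yes | No | Yes |
| Clinic visit | Yes | Yes | n/a |
| Question on Tool use and reason for non-use (5.3, 5.5) | Yes | None described | No |
| Interview about the encounter, users only (5.5) | Yes | None described | No |
| Note completed | Time not stated | Time not stated | n/a |
| Note reviewed, T2 and T3 (5.5) | Yes | Yes | n/a |

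The first two rows differ by arm by design, and their effect on the note is a Tool effect. The fourth and fifth rows also differ by arm but are not part of the Tool. The note's place in the sequence is open. Nothing in the protocol requires it to be signed before contact, limits scoring to text written before contact, or says how later addenda are treated. The by-arm comparison cannot separate the Tool's effect from that of the post-visit contact.

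**2. The plan's own figures**

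The protocol gives no expected rate, target difference or power for documentation. Its only sample-size figure is N = 76, for patient-reported discussion: 3% against 3% + 25 points = 28%, two-sided 0.05, 80% power, 30% attrition. The arcsine formula reproduces it:

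- h = 2·asin(√0.28) − 2·asin(√0.03) = 0.767
- n per arm = 2 × ((1.960 + 0.842)/0.767)² = 26.7
- total = 53.4/0.7 = 76.2

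Nothing below depends on this figure. Only the 3% and 28% discussion rates are borrowed, as two ends of a range.

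**3. What the artefact could be, under assumptions**

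Let

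- d = proportion of intervention visits with a real CKM discussion;
- Δ = increase, caused by the contact, in the chance that a real discussion is written down;
- f = proportion of notes still open at contact.

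Artefact added to the intervention arm = f × d × Δ.

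The documents give neither Δ nor f. The table assumes Δ = 10 to 30 points.

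| d | f = 1 | f = 0.5 |
|---|---|---|
| 3% | 0.3 to 0.9 points | 0.15 to 0.45 points |
| 10% | 1 to 3 points | 0.5 to 1.5 points |
| 28% | 2.8 to 8.4 points | 1.4 to 4.2 points |

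For example, 1 × 0.28 × 0.30 = 8.4 points. If no note is open at contact (f = 0), the artefact is zero. The table shows how the artefact scales. It is not evidence for any value of Δ.

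**The case against.** **The extra prompt may be small.** Before the visit, intervention providers already receive an email, a video link, a paper copy and a spoken reminder. One later question about Tool use, which does not mention charting, may add little, and the interview reaches users only. This stands, and it is why the effect may be modest. It does not make the contact part of the Tool.

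**Note timing is unknown.** A reader might infer that the comparison is biased and that staff step in immediately after the visit. The protocol supports neither. It says only that contact follows the visit, with email within a week as the fallback, and it is silent on when notes are written. The fallback does not remove the problem, since an email may also arrive before the note is complete.

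**Large figures are tempting.** If write-up is assumed to rise from 40–60% to 80–90% at a 28% discussion rate, the artefact is 0.28 × 0.20 = 5.6 to 0.28 × 0.50 = 14 points, which might be set against the 25-point target. The documents do not support that reading. The assumed jump is the very effect in question, all notes are taken to be open, and the lower write-up rate ignores the pre-visit prompts. The 25 points also belong to patient-reported discussion, not to documentation.

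**Other outcomes avoid patient report.** Attrition and provider-reported Tool use do. But attrition does not measure discussion, and Tool use is asked in one arm only.

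**Carry-over could dilute the difference.** Randomisation is by patient, so a questioned provider might later chart a usual-care patient differently. That would offset part of the effect. It does not act on the index note of the contacted visit.

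**Scoring rules may sit elsewhere.** The contact script and any abstraction rules are not shown. A scoring cut-off could properly be set in an analysis plan. The order of contact and note signing is a field procedure, which the protocol sets out without this safeguard.

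**Conclusion.** The point holds as an avoidable opening to bias in an additional outcome. Contact in one arm only, its role in recruitment and measurement, the by-arm use of the notes and the absence of a sequencing rule all follow from the text. For the index-visit note, the plausible direction is toward the Tool. The size cannot be derived from the documents. The illustrative range, 0.3 to 8.4 points with every note open at contact, rests wholly on the assumed 10 to 30 point increase in write-up, and it shrinks in proportion to the notes finished before contact.

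The T2 primary outcome, the patient's own report of the discussion, is not affected. A reader might also infer that the contact acts as a further reminder that inflates T3. The protocol gives no basis for sizing this, and the pre-visit prompts make it hard to argue that it adds much. The weight of the point is that the remedy is cheap and protects the one between-arm check on patient-reported discussion.

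**What to change.** Amend sections 5.3 (Recruitment Methods) and 5.5:

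- Make the Tool-use inquiry and the provider interview after the index-visit note is signed, where feasible. The first approach can be in person or by the encrypted email already allowed within a week. Phone is currently named only for the interview, so it is not an existing route for the Tool-use question.
- Where contact has to come first, record at that moment whether the note is signed.
- Score T2 documentation on note text that predates the contact. Report documentation that includes later text or addenda as a sensitivity analysis, so that genuine late entries are shown and not discarded.

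Cost: a signature or time-stamp check for each visit, slightly older provider recall, and possibly fewer in-person responses. The last matters in a feasibility study, which is why the sequencing is asked for where feasible and is backed by the scoring rule.
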